9.0 Study Population

9.1 Inclusion Criteria: Inclusion criteria for PWMC are as follows: 1) English speaking; 2) a physician diagnosis of early-stage Alzheimer's disease or mild-to-moderate cognitive impairment; 3) live in the community (including at home with or without the care partner, in a retirement community, etc.); 4) no history of serious mental illness (i.e., any major psychiatric disorder) and 5) must have some level of cellular connection in their place of residence (if known).

Care partners of PWMC must: 1) speak English; 2) be 21 years of age and over; 3) self-identify as someone who provides assistance to the PWMC because of their memory loss (these individuals are called "care partners," as these individuals may or may not provide the intensive hands-on care typical of "caregivers"); and 5) indicate a willingness to use the smartwatch system as well as to being randomized to a control group.

9.2 Exclusion Criteria: Those who do not meet the criteria above will be excluded.

Additionally, PWMC with severe or no dementia are not eligible.

9.3 Screening: Potential participants will complete a brief screening survey prior to enrollment, including items assessing each of the inclusion criteria listed above. Those who are considered eligible based on their responses will be invited to participate in the study. It is possible that potential participant informally screen as ineligible before completing a screener due to the natural progression of conversation via telephone or email. In these instances we would not continue to formally screener with those who we know are already ineligible.

In Phase II, PWMC will be administered the TICS-40 (Telephone Interview for Cognitive Status-developed for the Aging, Demographics, and Memory Study) via Zoom or the telephone during screening (50). The TICS-40 is a brief, 17-item screening tool, with scores ranging from 0 to 40, that is used to screen for different levels of cognitive impairment. According to a crosswalk between the Mini-Mental State Exam and the TICS-40, cutoff TICS-40 scores for mild dementia are 17-24, for moderate dementia are 6-16, and severe dementia are 0-5 (51, 52). Individuals with scores indicating presence of mild or moderate dementia (scores from 6 to 24) will be eligible to participate in the research. Individuals without the presence of dementia or with severe dementia will not be eligible.

10 Vulnerable Populations

10.1 Vulnerable Populations:

SOCIAL PROTOCOL (HRP-580)**PROTOCOL TITLE: A Mobile Informatics Solution to Aid in Memory****VERSION DATE: 7/1/2022**

Population / Group	Identify whether any of the following populations will be primary focus of the research (targeted), included but not the focus of the research or excluded from participation in the study.
Children	Excluded
Pregnant women/fetuses/neonates	included but not the focus
Prisoners	Excluded
Adults lacking capacity to consent and/or adults with diminished capacity to consent, including, but not limited to, those with acute medical conditions, psychiatric disorders, neurologic disorders, developmental disorders, and behavioral disorders	Primary focus of the research
Non-English speakers	Excluded
Those unable to read (illiterate)	Excluded
Employees of the researcher	Excluded
Students of the researcher	Excluded
Undervalued or disenfranchised social group	included but not the focus
Active members of the military (service members), DoD personnel (including civilian employees)	included but not the focus
Individual or group that is approached for participation in	Excluded

SOCIAL PROTOCOL (HRP-580)**PROTOCOL TITLE: A Mobile Informatics Solution to Aid in Memory****VERSION DATE: 7/1/2022**

research during a stressful situation such as emergency room setting, childbirth (labor), etc.	
Individual or group that is disadvantaged in the distribution of social goods and services such as income, housing, or healthcare.	included but not the focus
Individual or group with a serious health condition for which there are no satisfactory standard treatments.	included but not the focus
Individual or group with a fear of negative consequences for not participating in the research (e.g. institutionalization, deportation, disclosure of stigmatizing behavior).	Excluded
Any other circumstance/dynamic that could increase vulnerability to coercion or exploitation that might influence consent to research or decision to continue in research.	Excluded

10.2 Additional Safeguards:

The smartwatch technology being tested in this study is designed to be used by persons with mild-to-moderate dementia severity. Testing the feasibility and utility of the technology for persons with mild or moderate cognitive impairment is therefore an important research objective. It is anticipated that the technology will be most useful to individuals whose memory has deteriorated enough to benefit from the cues and reminders provided by the smartwatch. Therefore, moderate cognitive impairment may represent the least degree of impairment compatible with the aims of the study. By including participants with mild-to-moderate cognitive impairment, we will learn whether the technology is feasible for various stages of cognitive impairment, whether the technology provides improvements in social interactions, and whether there are modifications that might improve the utility of the technology for PWMC.

Due to the natural progression of AD/ADRD and the length of the study, PWMC will be reassessed for their capacity to consent and re-assent or re-consent to participate in

SOCIAL PROTOCOL (HRP-580)

PROTOCOL TITLE: A Mobile Informatics Solution to Aid in Memory

VERSION DATE: 7/1/2022

the research at 3- and 6-month time points. We will use the UCSD Brief Assessment of Capacity to Consent to determine whether participants are capable of providing consent for themselves. Those who are not able to provide consent will be asked to re-assent to participate, in which case, assent will be documented by asking the participant to verbally sign an assent form (attached). Those who are able to provide consent will be asked to re-consent to participate using the brief follow-up consent form (attached).

Since the study involves no invasive procedures, there will be no physical risks to study participants. Thus, no research-related injuries need to be disclosed as none are expected. The consideration of need is potentially stressful, and thus there are possible psychological risks for the PWMC and care partners. However, the research team has considerable experience providing psychosocial support to Alzheimer's disease and related dementia caregivers on various research protocols, so serious psychological risks are unlikely to occur based on this experience. The potential social or legal risks for the participants relate only to possible violations of confidentiality.

Participants with impaired capacity to consent will be closely monitored when first introduced to the smartwatch technology and taught how to use it; given that this technology is non-invasive, additional monitoring in Phase II will take place at the 3- and 6-month survey interviews. Participants with memory concerns will be withdrawn from the study if they appear unduly distressed.

We will use the UCSD Brief Assessment of Capacity to Consent to determine whether participants are capable of providing consent for themselves. Those who are not able to provide consent personally will be asked to assent to participate. In that case, assent will be documented by asking the participant to verbally sign an assent form (attached). All potential participants will be informed of the research objectives and procedures to the greatest extent that is compatible with their understanding.

Though not specifically targeted for inclusion, participants from some of the above groups (indicated in the table) may be allowed to participate, as indicated in the table. Participants will be reminded that all study procedures are voluntary and will not impact the care they receive from any institution. We do not anticipate any individuals from the above noted groups to have increased risk from participating in the proposed research, such as an increased risk of coercion, etc. Thus, our standard protocol practices (i.e. data security, confidentiality procedures, etc.) provide reasonable protections to these vulnerable participants.

The research does involve cognitively impaired adults, or adults with fluctuating, diminished, or lacking capacity to consent, this the ([CHECKLIST: Cognitively Impaired Adults \(HRP-417\)](#)) below has been reviewed.

10.2.1 This population must be included in the research study because they are part of the target population. By including this population in the research, we will learn whether or not the Smartwatch Reminder technology is

SOCIAL PROTOCOL (HRP-580)

PROTOCOL TITLE: A Mobile Informatics Solution to Aid in Memory

VERSION DATE: 7/1/2022

helpful to PWMC and in what ways it may be helpful to them, as well as their care partners.

10.2.2 Persons with Memory Concerns are being included in the study if they have the capacity to consent or not, because we need to know if individuals with lesser and higher degrees of cognitive impairment benefit from the SR or not. Individuals with severe cognitive impairment, such as late-stage dementia are not included in our study because we do not expect the SR to provide any benefit to this group.

10.2.3 Adults lacking the capacity to consent or have a diminished capacity to consent are one of the primary groups of participants to be recruited to the study. Specific safeguards to protect this population include signing of a consent form by their family caregiver. Additionally, the person with memory loss either consents or assents to the research before each survey based on their Capacity to Consent scores – see more detail in the consent section below.

10.3 If research includes potential for direct benefit to participant, provide rationale for any exclusions indicated in the table above:

Some individuals in the above vulnerable groups are excluded because they are not our population of interest (i.e. ADRD does not impact children) or because participating in such research would potentially be risky for them or because they would be ineligible (i.e. must live in the community therefore prisoners would be ineligible).

11 Number of Participants

11.1 Number of Participants to be Consented:

Phase I: 20 dyads, or 40 participants

Phase II: 100 dyads, or 200 participants

12 Recruitment Methods

12.1 Recruitment Process: Participants will be recruited in various in-person and online ways using the approved text and images. In person recruitment opportunities may include advertisements at memory clubs and programs for PWMC, through the Care Options Network, and at the annual Caring for People with Memory Loss Conference. Additionally, virtual recruitment via advertisement in the University of Minnesota Caregiver Registry and via newsletters shared by colleagues and professionals in this area of work are engaged with the target population. The research coordinators, [name], [name], [name], or [name] will initiate email, telephone, or mail contact with family members on the Registry and who respond to an advertisement, or those who complete a permission to contact form

SOCIAL PROTOCOL (HRP-580)

PROTOCOL TITLE: A Mobile Informatics Solution to Aid in Memory

VERSION DATE: 7/1/2022

(sent out via emails, shared at the conference, via newsletters, etc.; attached). In addition, [name], [name], [name], or [name] will ask professional care providers on the Registry to identify potential family members for recruitment purposes, including family members of diverse ethnic or racial origin and geographic location (given that many provide care to under-represented older persons).

Snowball recruitment among potential/enrolled participants may also be used. In this case, following the initial screening conversation, potential participants may be asked if they know of anyone else who might be fitting for the study. If so, UMN staff will share an approved flyer for the [potential] participant to then share. If needed, participants will be recruited via ads on facebook and newspapers, on the National Institutes of Health-supported website called researchmatch.org, and other national research recruiting sites and registries fitting for this population (such as Banner Health and FTD Disorders Registry LLC). Using this method, only those who are interested are contacted.

Registration forms for educational presentations (by study staff or other agencies) may include an opportunity for individuals interested to provide their permission for the research team to contact them to share additional information about the study.

[Thus, by nature of this, UMN staff or other agency staff involved in planning, hosting, or post-webinar certificates will have access to the names/contact information of those indicating interest in receiving more information about the study]. Presentation “polls” may offer an additional opportunity for presentation attendees to provide permission for contact. Presentation slides may also be used during these community presentations to increase outreach. Hard copy permission forms may also be presented at in-person presentations.

Note: General promotional materials/text (emails/newsletters/flyers/etc) are shared in the context of general promotional recruitment efforts. However, study staff do not pursue individualized study-related contact with potential participants until contact is made by an interested individual or a permission form/request for information is obtained.

12.2 Source of Participants: Participants will be community members who respond to a recruitment source listed in 12.1. [name] and his evaluation team developed and actively maintain the Caregiver Registry based on their community outreach and education efforts on Alzheimer’s disease and related dementias. All individuals in the Registry have provided permission for [name] and his team to contact them to participate in research. The registry includes 675 family members of PWMCs and 316 professionals as of August 2018, and calls for new registry participants occur annually from March to June.

12.3 Identification of Potential Participants: Individuals will self-identify as potential participants. [name] has developed and maintains the University of Minnesota Caregiver Registry based on his various community outreach and education efforts on Alzheimer’s disease and related dementias (#1007S85812). All individuals in the Registry have provided permission for [name] and his research staff to contact

SOCIAL PROTOCOL (HRP-580)

PROTOCOL TITLE: A Mobile Informatics Solution to Aid in Memory

VERSION DATE: 7/1/2022

them to participate in research. [name] has conducted several prior and ongoing evaluations of early-stage dementia support programs throughout the Minneapolis/St. Paul area and works with several memory clubs and programs for PWMC. [name] also directs the Center for Healthy Aging and Innovation which hosts events among our target population, which may also be used for recruitment. Finally, [name] is a member of the Care Options Network, and will post an invitation to participate to Network members. No medical records will be used to identify potential participants.

12.3.1 For information contained in private/protected records, explain how the researcher has legitimate access to these records: N/A

12.3.2 [name], [name], [name], [name], the research coordinators, or the research assistant will make initial contact with potential participants who respond to advertisements or complete a permission to contact form.

12.3.3 No medical records will be used to identify potential participants.

12.4 Recruitment Materials: Flyers, emails, ads, and phone calls will be used for recruitment. A copy of the flyer and email/phone script are included in the IRB application.

12.5 Payment: In order to provide additional rapport and incentive to participate, all care partner and PWMC dyads in the proposed project will be provided with up to a \$100 participation incentive. Those who are selected and complete a semi structured interview will be provided an additional \$50 participation incentive. Compensation will be mailed after completion of participation (following the dyadic interview for Phase I, and after the 6 month assessment for Phase II). For phase II, dyads will receive a prorated amount based on the number of surveys completed (\$33.00 for one, \$66.00 for two, or \$100.00 for all three) The dyads will be compensated using Amazon gift cards.

13 Withdrawal of Participants

13.1 Withdrawal Circumstances: If instances of elder abuse or mistreatment are identified or reported to the research team, the Minnesota Adult Abuse Reporting Center will be contacted ([name]) and the participant will be withdrawn from the study without their consent.

Withdrawal Procedures: In instances where care partners or PWMCs wish to withdraw from the study, we will determine the reason for study withdrawal, and whether or not the care partner or PWMC agrees to still complete regular, brief surveys (either online or over the phone) to collect data on outcome variables. Data prior to withdrawal will be used in subsequent analyses unless the dyad does not wish for their data to be included at all.

SOCIAL PROTOCOL (HRP-580)

PROTOCOL TITLE: A Mobile Informatics Solution to Aid in Memory

VERSION DATE: 7/1/2022

13.2 Termination Procedures: Following completion of the Phase II study period, participants will be asked to return the SR technology to the research team. We will thank them for participating and distribute compensation. After all participants have completed their study period, we will clean and analyze the data, and generate reports of the findings. Data will be securely stored for 5 years or until all dissemination efforts have been completed.

14 Risks to Participants

14.1 Foreseeable Risks: Since the study involves no invasive procedures, there will be no physical risks to study participants. The consideration of need is potentially stressful, and thus there are possible psychological risks for the PWMC and care partner. Since research team has considerable experience providing psychosocial support to Alzheimer's disease and related dementia caregivers on various research protocols, serious psychological risks are unlikely to occur. The potential social or legal risks for the participants relate only to possible violations of confidentiality.

Complete privacy cannot be guaranteed while using Zoom video conferencing, as some tools keep participant data, and we cannot guarantee others are not keeping a log of the discussion. Additional steps will be taken by password protecting these dyadic interviews.

The experience of the University of Minnesota research team will minimize the possibility of psychological risks. The unlikelihood of such problems is evident from the absence of any clinically significant problems during the past fifteen years that [name] has operated various protocols related to dementia caregiving research. Additionally, as another safeguard, participants will receive a list of ADRD and caregiving resources (approved) at each time point with their baseline and follow-up surveys, during a time where sensitive questions may prompt emotional responses related to current and future situations. RA will be trained to interview in ways that are non-threatening, friendly, and respectful. We will emphasize to all participants that they do not have to complete any question they do not want to answer, and that the interview may be terminated at any time according to their wishes. We will stress to care partners or PWMCs that their decision to discontinue the study will in no way affect the services they are receiving from the University of Minnesota or other entities.

In the event a care partner or PWMC does become upset during the interview process, the RA will contact the PI who will be available for consultation. If a participant is in crisis because of their care situation or some other reason, research staff will be instructed to consult with the PI. With the participant's permission, we will then contact the appropriate resource person in an external agency (e.g., the Alzheimer's Association). Based on the research team's experience working with caregiving families, we expect no or very few such instances to occur. If a member of the research team does identify neglect or other potentially inappropriate care practices, the state Ombudsman will be notified to protect the rights of persons with dementia and their families.

There is a possibility that data collected by AME from the technology, such as location, could be lost. This is very unlikely to occur, but participants will be made aware of this risk prior to consenting.

SOCIAL PROTOCOL (HRP-580)

PROTOCOL TITLE: A Mobile Informatics Solution to Aid in Memory

VERSION DATE: 7/1/2022

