audit trail). In addition, patterns that link particular themes will be identified and discussed in successive meetings between [name] and [name] to identify more complex processes of Smartwatch use or this technology's pathways to benefit PWMC and their care partners. During monthly team meetings, the development of codes, categories, and themes will be reviewed with the other academic investigators (Drs. [name] and [name]) and the AME team to yield any additional input into these project components. The multiple team meetings and discussions will allow for an exploration of alternative interpretations of the qualitative data and will also provide a check regarding the quality and richness of the data collected during the embedded mixed methods components.

Phase II Quantitative Analysis: Data available at baseline and 6 months will allow for a 2x2 repeated measures analysis of covariance to examine whether use of the SR results in statistically significant changes in PWMC negative health transitions and , social interaction, pleasant events, social stress, loneliness, , relationship closeness, and community engagement and care partner well-being, such as social support, depression and burden (9). The primary independent variable in the proposed investigation consists of an indicator variable for random assignment into the SR treatment condition or the attention control group. IBM SPSS Statistics 21(41) will be used to conduct these analyses, as it supports a range of univariate, bivariate, and multivariate statistical analysis procedures. The team has extensive experience conducting longitudinal analyses on their prior research on dementia(5, 6, 42-44). Our proposed analyses will provide in-depth tests of the study hypotheses. Outcomes will include statistical significance of within-subjects, or 6-month change, in those in the Smartwatch Reminder treatment or control groups on key outcome variables (see above). Additional analyses will determine if covariates (context of care, mobile device proficiency, and dementia severity indicators) significantly vary across the SR treatment and attention control groups at baseline and over 6-months. If statistically significant variations between the SR treatment and control groups are found, baseline and/or change scores for these covariates will be included in all repeated measures analyses of covariance tests to provide additional statistical control.

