Phase II: A repeated measures analysis of covariance (ANCOVA) will be utilized to capitalize on the randomized design and the two sets of data that will be collected. The number of PWMC-care partner dyads to be enrolled to address study hypotheses was determined using power analysis procedures(45, 46). A sample size of 100 to identify a medium statistical effect (standardized regression coefficient = 0.15) at a suitable level of statistical power (0.80 is considered an excellent power value) is able to effectively incorporate up to 6 baseline covariates that vary significantly across the randomly assigned Smartwatch Reminder treatment and control conditions if they exist (as random assignment is often used to ensure statistically comparable treatment and control conditions, we feel this is a conservative estimate of baseline covariates)(46). Specifically, we relied on statistical power tables by the expert statistician Cohen(46) to conduct our assessment of power. As noted in Table 2 of Cohen (1992)(45), an alpha level of .05, a medium effect size of .15 (as opposed to using specific measures, Cohen operationalized a medium effect size of .15 as one that is observable, and a survey across the social sciences suggested that this proposed effect size was close to the average of observed effects), and a multiple regression model (similar to an ANCOVA) that includes up to 6 covariates requires a sample size of 97. For these reasons, an expected sample size of 100 PWMC and care partner dyads will be sufficient to conduct the Phase II efficacy evaluation. We anticipate having less than a 3% attrition rate which will ensure we maintain sufficient power. As noted in various recommendations for mixed methods sampling, 20 participants is considered an adequate sample size for semi-structured interview protocols to ensure the richness and depth of open-ended data collected(36, 47).

17.3 Statistical Analysis:

Statistical analyses used will include calculation of frequencies, bivariate correlations, t-tests, chi-square tests, and repeated measures ANCOVA as detailed above.

17.3 Data Integrity:

SOCIAL PROTOCOL (HRP-580)

PROTOCOL TITLE: A Mobile Informatics Solution to Aid in Memory

VERSION DATE: 7/1/2022

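### Section 10.2.2 says the trial needs to know whether less and more impaired PWMC benefit, but the plan gives no randomised estimate by severity; one low-precision exploratory TICS-40 analysis would

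*Combined protocol and SAP*

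**What the plan says.** **Why both severities are enrolled.** Section 10.2.2 explains the inclusion of PWMC regardless of capacity to consent: "we need to know if individuals with lesser and higher degrees of cognitive impairment benefit from the SR or not". Section 10.2 expects the watch to help most once memory has declined far enough, and adds that "moderate cognitive impairment may represent the least degree of impairment compatible with the aims of the study".

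**Who enters.** Section 9.3 uses the TICS-40: "Individuals with scores indicating presence of mild or moderate dementia (scores from 6 to 24) will be eligible". The mild band is 17-24 and the moderate band 6-16.

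**How the effect is estimated.** Sections 3.1 and 17.1 specify a 2x2 repeated measures ANCOVA (arm by time, baseline and 6 months) on the whole sample. Severity appears in one place: "Additional analyses will determine if covariates (context of care, mobile device proficiency, and dementia severity indicators) significantly vary across the SR treatment and attention control". Covariates that differ significantly are then added to the models. No arm-by-severity term or severity subgroup is planned.

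**What else touches severity.** Section 17.1 adds analyses of SR use and context of care, confined to the SR arm. Section 5.2 selects 20 SR-arm dyads for interview, partly by severity.

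**The concern.** Adjusting for severity does not show whether the effect of the SR varies with it. The adjusted analysis still returns one average effect, and under the plan even that adjustment happens only when a baseline test is significant. A plan followed to the letter would therefore finish without a randomised estimate for either severity band, although the protocol gives that knowledge as a reason for including people who may lack capacity to consent.

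The protocol also gives its own reason to expect a gradient. If benefit is concentrated in moderate PWMC, a null pooled result could conceal it. If the pooled result is positive, nothing planned would show whether both bands share in it. The information needed is already in hand, because the TICS-40 is administered at screening, before randomisation.

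**Working it through.** **1. The plan's own figure.** Section 17.2 uses "an alpha level of .05", power of 0.80, "a medium effect size of .15" and a regression that "includes up to 6 covariates requires a sample size of 97". Treating 0.15 as f² for the joint test of six predictors (noncentral F, u = 6, v = N − 7, λ = 0.15N), the exact requirement is N = 98, and power at N = 97 is 0.798. The figure reproduces. It is a calculation for the joint R² of six predictors and says nothing about variation of the SR effect with severity.

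**2. Does any planned analysis give benefit by severity?**

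| Element | Randomised contrast? | Severity as effect modifier? |
|---|---|---|
| 2x2 ANCOVA (3.1, 17.1) | Yes | No |
| Covariate rule (3.1, 17.1) | Yes | No: adjustment only, if arms differ |
| SR use and context of care (17.1) | No: SR arm only | No: context of care is listed apart from dementia severity in 5.2 |
| Interviews (5.2) | No: 20 SR-arm dyads | Sampled by severity, qualitative |

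No row has both.

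**3. What a severity analysis could deliver.** From the documents: 100 dyads, 1:1. Assumed: outcome SD scaled to 1, baseline-outcome correlation r = 0.5, half the sample mild (share m = 0.5), two-sided 5% tests. Two readings of the planned test are possible:

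- Baseline-adjusted: SE = (2/√100) × √(1 − r²) = 0.20 × √0.75 = 0.173.
- Arm-by-time as a change-score contrast: SE = (2/√100) × √(2(1 − r)) = 0.20 × 1 = 0.20.

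Band SE = SE/√0.5. Interaction SE = SE × √(1/m + 1/(1 − m)) = 2 × SE.

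| | Baseline-adjusted | Change score |
|---|---|---|
| Pooled SE | 0.173 | 0.20 |
| SE per band | 0.245 | 0.283 |
| Interaction SE | 0.346 | 0.40 |
| 95% CI half-width, band (1.96 × SE) | 0.48 | 0.55 |
| 95% CI half-width, interaction | 0.68 | 0.78 |
| Power, 0.5 SD interaction: Φ(0.5/SE − 1.96) | 30% | 24% |

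With a 30/70 mix the interaction SE rises to 0.378 or 0.436. For 80% power on a 0.5 SD interaction, N = 16 × (2.802/0.5)² ≈ 502 on the change-score reading, or 502 × 0.75 ≈ 377 baseline-adjusted. The figures are for a two-band contrast; a continuous TICS-40 term may do somewhat better, depending on a score distribution the documents do not give.

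**4. Illustration of masking (all inputs assumed).** Suppose moderate PWMC gain 0.5 SD and mild PWMC gain nothing. Pooled effect = 0.5 × (1 − mild share).

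| Mild share | Pooled effect | Power, SE 0.173 | Power, SE 0.20 |
|---|---|---|---|
| 0 (undiluted) | 0.50 | 82% | 71% |
| 30% | 0.35 | 52% | 42% |
| 50% | 0.25 | 30% | 24% |
| 70% | 0.15 | 14% | 11% |

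**The case against.** **The severity question is not a trial aim.** Aim 4 and the Phase II overview in Section 5.2 ask about benefit overall, and the pooled contrast answers that. Section 10.2.2 is a rationale for including a vulnerable group. Sections 5.1 and 10.2 attach severity mainly to feasibility and utility, on which the interviews, usage logs and system review do bear. This stands. It limits the point to an unmet inclusion rationale. It does not remove it, because none of those sources has a control group. The interview split (middle versus late stage) also does not match the mild and moderate entry bands.

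**The gradient is uncertain.** The sentence in Section 10.2 is hedged. Section 2.3 notes a limited ability to learn new information and Section 10.2.2 expects no benefit in severe impairment, so benefit could favour mild PWMC instead. This also stands. The masking table is an illustration and not a forecast. An unknown direction is itself a reason to estimate the gradient.

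**The remedy is underpowered.** True: step 3 shows it. It is useful as one pre-specified estimate with its interval, which is easier to interpret than an unplanned subgroup result.

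**Stronger readings that the documents do not support.** A reader might infer that a positive pooled result says nothing about mild PWMC. It says something, because they are in the randomised sample; it is only not band-specific. A reader might also infer that the single unstratified list in Section 5.2 undermines a severity comparison. It does not: it only permits chance imbalance, which adjustment for TICS-40 addresses, and re-stratifying late in recruitment would add little.

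**Conclusion.** The point holds in a limited form. The plan as written produces no randomised estimate of SR benefit by severity, although Section 10.2.2 gives that as a reason for whom it enrols. The pooled comparison remains valid for the overall question. Whether it masks a difference, and by how much, cannot be determined from the documents, which give neither the mild/moderate mix nor an expected gradient.

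A severity analysis at this sample size is estimation only. At 100 dyads, r = 0.5 and an even mix (the last two assumed), the SE is about 0.25-0.28 SD per band and 0.35-0.40 SD for the interaction, so a difference of 0.5 SD could be neither confirmed nor excluded. A reader might infer that the trial should be able to settle the question; that would need several hundred dyads, and nothing in the plan promises it.

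**What to change.** In Section 17.1:

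1. Include screening TICS-40, as a continuous score, in every Phase II efficacy model whatever the baseline balance. For this covariate, that replaces the significance-gated rule.
2. Pre-specify one exploratory arm-by-TICS-40 term for one named social-interaction outcome. Section 5.2 makes social interaction the SR's primary goal but lists frequency, duration and satisfaction over several contact modes, so the sponsor must name the measure.
3. Report the SR effect with a 95% confidence interval in the mild (17-24) and moderate (6-16) bands, labelled as estimation, with a statement of the low precision worked out above.

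Separately, reconcile the statement in Section 10.2 on the least compatible degree of impairment with the entry range in Section 9.3.

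The cost is wording, one covariate per model (within the six that Section 17.2 allows for) and one interaction term. No new data are needed. The change should be made before outcomes are compared by arm. The drawback is wide band-specific intervals, which must not be read as evidence for or against benefit in either band.
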